1.1.2 Secondary Objectives

- To compare cladribine + rituximab vs. cladribine alone in terms of 1) initial MRD-free survival and disease-free survival, 2) response to delayed rituximab for relapse, to determine if early rituximab compromises later response, and 3) feasibility of administration as an outpatient by simultaneous rituximab beginning before the cladribine in nonrandomized HCL patients.
- To determine if MRD levels and tumor markers (soluble CD25 and CD22) after cladribine and/or rituximab correlate with response and clinical endpoints.
- To compare blood MRD-free survival in patients who receive cladribine and up to 2 courses of rituximab, with respect to whether the 1st course of rituximab was used simultaneous with cladribine.
- To determine, using MRD and tumor marker data, when bone marrow biopsy (BMBx) can be avoided in managing HCL.
- To compare response and MRD after the 1st and 2nd courses of cladribine.
- To evaluate the effects of cladribine and rituximab on normal T- and B-cells.
- To enhance the study of HCL biology by cloning, sequencing and characterizing monoclonal immunoglobulin rearrangements.

- To determine overall survival, particularly in patients with poor-prognosis HCL like HCLv.
- To correlate bone marrow MRI signal with bone marrow biopsy

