1.3.2 Endpoints to test simultaneous vs. delayed rituximab

The primary endpoint is whether simultaneous cladribine and rituximab cause a lower rate of MRD at 6 months than cladribine alone. Based on studies of rituximab for MRD after CdA [41, 47], CR

without MRD should be achieved in > 90% at 6 months after cladribine + rituximab. CR without MRD should be about 40-60% after cladribine alone, depending on whether or not patients had prior cladribine [11, 39, 40, 42-46]. However, a significant difference at 6 months would not indicate superiority in the clinical outcome of simultaneous cladribine + rituximab over cladribine alone, since delayed rituximab after 6 months might work better if it had not been used previously. Therefore, the major secondary endpoint will be to assess blood MRD-free survival not only after cladribine, but also after up to 2 rituximab courses given if needed for MRD in blood. BMBx IHC, blood and bone marrow aspirate FACS will be used for detecting MRD for the primary endpoint. However, since non-compliance with BMBx is expected to increase with longer follow-up, MRD-relapse for the secondary endpoints for need for delayed rituximab will need to be determined by blood tests, either blood FACS positivity or presence of cytopenias (ANC < 1500/ul, Plt < 100,000/ul, or Hgb < 11 g/dl). Patients FACS-negative in both blood and bone marrow aspirate are considered in MRD-negative CR regardless of blood counts. FACS, consensus PCR and IHC are all CLIA certified tests. Patients with 'dry' bone marrow or bone marrow unable to be aspirated will be considered MRD+, since in MRD-free CR, the bone marrow aspirate should be liquid and able to be aspirated. RQ-PCR, which is the most sensitive test, will also be observed, but will not be used for clinical decisions or statistics because it is early in its development, particularly in following HCL after chemotherapy. If patients achieve significantly longer time MRD-free survival after cladribine + rituximab than after cladribine alone, but shorter MRD-free survival after delayed rituximab if rituximab was used previously with cladribine, this will argue against changing the standard treatment for HCL from cladribine alone. The delayed rituximab in the trial design also permits several secondary scientific objectives (see Section 1.1.2) to be investigated for rituximab alone, including 1) determining if MRD levels and tumor markers (soluble CD25 and CD22) after rituximab correlate with response and tumor burden, 2) determining if BMBx can be avoided for judging response in HCL after rituximab, and 3) determining the effect of rituximab on normal B-cells without interference from simultaneous or recent cladribine.

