
1.3.3 Inability to assume that rituximab should be used with cladribine

Before a trial begins it is optimal for neither arm of a randomized trial to be obviously more advantageous than the other. There are potential advantages and disadvantages of simultaneous vs. delayed rituximab. It is possible, for example, that rituximab could have been more effective when begun at least 6 months after cladribine than concurrently, because by that time masses of tumor cells in the marrow, spleen and lymph nodes, which would present a tumor penetration problem for the rituximab Mab, might be at their minimum size. Secondly, if simultaneous rituximab were to fail to eliminate MRD, it could select for cells deficient in apoptosis and render patients unresponsive to rituximab and other agents when relapse occurs later in the disease course. Moreover, it is possible that the risk of infection could increase with combined use of rituximab and cladribine, since rituximab is known to cause rapid and prolonged (3-6 month) depletion of normal B-cells [57]. While this may not be a significant problem after single-agent short-course rituximab, it may be more problematic with the longer 8-cycle course, particularly after cladribine. Thus, a randomized trial was needed to determine if rituximab should be used with cladribine or delayed until after MRD appears. At this time, it is not considered standard to combine rituximab with cladribine for first-line or second-line treatment of HCL.

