1.3.4 Need to assign patients with regard to prior purine analog

Based on CR rates of 91 and 62% for cladribine in patients with 0 and 1 prior courses of cladribine, respectively [8], response in this trial, including MRD endpoints, may likely be related to whether or not patients received prior cladribine or the other purine analog pentostatin. Therefore, patients need to be separated into two groups prior to randomization. This trial may result in a recommendation that cladribine + rituximab become the standard treatment only for newly diagnosed HCL, or only for HCL with 1 prior cladribine or pentostatin course, or for both groups, or for neither. Prospective randomization should facilitate the validity of such recommendations.

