3.2.2 Rituximab

Rituximab 375 mg/m² i.v. infusion every week x8, begin day 1 in half of randomized patients and in all HCLv patients, and then again in all patients at least 6 months later when HCL is detected by blood FACS. Patients who first received rituximab at least 6 months after cladribine may receive a 2nd course of rituximab at the same dose and schedule at least 6 months after the beginning of the 1st course, if and when HCL is detected again by blood FACS. When rituximab is given on the same day as cladribine (day 1), it will be given at the end of the 2-hour infusion of cladribine. In the 25 nonrandomized newly-diagnosed HCL patients beginning rituximab prior to cladribine, the 2 hour infusion of cladribine will be begin at the end of the infusion of rituximab. Actual body weight measured within 4 weeks prior to initial treatment with rituximab will be used for calculations of body surface area.

It is possible, though uncommon for HCL and HCLv to change phenotype. This would be considered a second malignancy which would require patients to be taken off-treatment. However, we feel it is justified for these patients to remain on study and continue to receive treatment despite the development a new clone (second malignancy) because they are likely to receive on-going benefit from the treatment. Thus, at the discretion of the PI, these patients may continue with treatment including delayed Rituximab if appropriate.

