6 STATISTICAL CONSIDERATIONS

6.1 PRIMARY ENDPOINT

The primary objective of this trial is to determine if the rate of minimal residual disease (MRD) identified in patients 6 months after beginning cladribine for treatment of HCL differs according to whether cladribine is combined with rituximab. Half of the randomized patients receive cladribine and rituximab concurrently, and all patients receive delayed rituximab at least 6 months after cladribine, if and when MRD is detected. Patients with blood-MRD at least 6 months after delayed rituximab may also receive a 2nd course of delayed rituximab if they did not receive rituximab simultaneous with cladribine. The most important secondary objectives are MRD-free

survival after cladribine, and MRD-free survival after delayed rituximab or after up to 2 courses of rituximab. MRD studies for the primary endpoint will be limited to 1) blood FACS, 2) bone marrow aspirate FACS and 3) BMBx IHC, so that patients will be considered MRD+ if any of these 3 tests is positive. Of these tests, only blood FACS will be used for triggering delayed rituximab, because it is the most sensitive test of MRD in blood and bone marrow results will be affected by compliance for the procedure. Blood and marrow RQ-PCR will also be studied but will not be used for the primary endpoint because RQ-PCR though extremely sensitive is too early in its development as an MRD study. All MRD studies except for RQ-PCR are performed in CLIA certified labs. If the patient has a non-HCL monoclonal population in the blood, including but not limited to monoclonal B-cell lymphocytosis (MBL) and monoclonal gammopathy of uncertain significance (MGUS), the blood or marrow PCR or RQ-PCR may be false-positive so these PCR tests are not evaluable for the primary endpoint.

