6.2 SECONDARY ENDPOINTS

In addition to the primary goal of determining differences in the MRD level according to rituximab administration, the following goals will also be explored in patients on this study.

The most important secondary endpoints are MRD-free survival after cladribine, and MRD-free survival after up to 2 courses of rituximab. For the secondary endpoints of this protocol, and for triggering delayed rituximab, patients with or without CR are considered MRD+ if the blood FACS is positive or if low blood counts become inconsistent with CR (ANC < 1500/ μ l, Plt < 100,000/ μ l, or Hgb < 11). Patients FACS-negative in both blood and bone marrow aspirate are considered MRD-negative regardless of blood counts. Failure of cladribine and/or rituximab to clear MRD by blood FACS requires that this test be positive at 6 months since MRD at 1-3 months may clear by 6 months. However, MRD relapse will be considered when first detected, even if before 6 months, if cladribine and/or rituximab fail to clear MRD at 6 months. If simultaneous cladribine and rituximab is superior to cladribine and delayed rituximab, MRD-free survival after cladribine and after delayed rituximab should together be longer if cladribine was combined with rituximab than if used alone. In order to compare the probability of development of MRD as a function of time according to whether rituximab is used immediately or not, Kaplan-Meier curves for this endpoint will be created, beginning at the date of randomization, and compared using a two-tailed log-rank test. Patients who develop MRD will be considered to have had an event for the actuarial curve, while those without MRD found in this manner will be considered censored and will remain in follow-up for this endpoint. With each stratum considered separately, or if both strata are combined, the power for this comparison will potentially be low, but the results may demonstrate a trend if one is present. Measurement of best response to cladribine vs. cladribine + rituximab will also be done at 1 and 6 months after cladribine. The CR and PR rates will be reported, as well as appropriate 95% exact confidence intervals.

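### Section 1.3.2 lets outcome after delayed rituximab count against early rituximab, although that contrast is between patients selected after randomisation and can be biased either way

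*Combined protocol and SAP*

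**What the plan says.** Section 1.3.2 describes a pattern and how it will be read: if the combination gives significantly longer MRD-free survival "but shorter MRD-free survival after delayed rituximab if rituximab was used previously with cladribine, this will argue against changing the standard treatment". Section 1.1.2 lists the same contrast as a secondary objective with a causal purpose: "response to delayed rituximab for relapse, to determine if early rituximab compromises later response". Section 1.3.3 gives the feared mechanism: "if simultaneous rituximab were to fail to eliminate MRD, it could select for cells deficient in apoptosis and render patients unresponsive to rituximab". Section 1.3.4 says what may follow from the trial: "This trial may result in a recommendation that cladribine + rituximab become the standard treatment only for newly diagnosed HCL", or for the previously treated group, both or neither.

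Who receives delayed rituximab is set in 3.2.2 ("and then again in all patients at least 6 months later when HCL is detected by blood FACS") and 6.1 ("all patients receive delayed rituximab at least 6 months after cladribine, if and when MRD is detected"). Section 6.2 also admits low blood counts as a trigger. On any of these wordings, a patient must first be found MRD-positive.

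The plan also contains a comparison that keeps the randomised groups. The third objective in 1.1.2 compares blood MRD-free survival over cladribine and up to two rituximab courses, by whether the first course was simultaneous. Section 1.3.2 says "the major secondary endpoint will be to assess blood MRD-free survival not only after cladribine, but also after up to 2 rituximab courses". Section 6.2 expects that, if simultaneous treatment is superior, "MRD-free survival after cladribine and after delayed rituximab should together be longer if cladribine was combined with rituximab than if used alone", and starts its Kaplan-Meier curves at randomisation. It labels everything other than the primary comparison exploratory.

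**The concern.** A contrast restricted to patients who became MRD-positive is not protected by randomisation. Entry depends on an outcome that early rituximab is designed to alter. Recipients in the early arm have failed cladribine plus rituximab; recipients in the control arm have failed cladribine alone. The first half of the 1.3.2 pattern, that the combination works, is also the condition under which the two groups are filtered differently. No section mentions this.

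At stake is interpretation. If the 1.3.2 sentence is applied as it stands, a difference produced by selection could be taken as evidence that early rituximab spoils later response, and could weigh in the standard-treatment recommendation that 1.3.4 anticipates.

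**Working it through.** **1. The plan's own figures.** The point disputes no figure, but the rates in 6.1 show how unequal the filtering may be. Exact one-sided Fisher power at 0.1 is 80.6% for 34 per arm (5% v 25%) and 80.3% for 31 per arm (10% v 35%), which agrees with the stated 80%. At those rates the expected numbers MRD-positive at 6 months are:

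| Stratum | Early arm | Cladribine alone |
|---|---|---|
| 0 prior courses | 34 × 0.05 = 1.7 | 34 × 0.25 = 8.5 |
| 1 prior course | 31 × 0.10 = 3.1 | 31 × 0.35 = 10.85 |
| Both (65 per arm) | 4.8 | 19.35 |

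Later relapses add to these, at rates the documents do not give.

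**2. Model with no carry-over harm.** None of these inputs comes from the documents. Median MRD-free time is 60 months after any course containing rituximab, so λ = ln 2 / 60 = 0.01155 per month. The rate after cladribine alone is kλ, with k = 4 or 2. There are 96 months in which to become MRD-positive and 60 months of follow-up after the delayed course. Gamma frailty z has mean 1 and variance 0.25, 0.5 or 1. The second-period rate is λz in both arms, so earlier rituximab has no effect on it.

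**3. Mechanism by hand (variance 1, k = 4).** Let Λ be the cumulative rate to 96 months: 0.01155 × 96 = 1.109 in the early arm and 4 × 1.109 = 4.436 in controls. With shared frailty the proportion becoming MRD-positive is Λ/(1+Λ), giving 65 × 0.526 = 34 early and 65 × 0.816 = 53 control. The mean frailty of those selected is 1 + 1/(1+Λ):

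- early: 1 + 1/2.109 = 1.474
- control: 1 + 1/5.436 = 1.184
- ratio: 1.474 / 1.184 = 1.25, against early rituximab, with no harm present

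If the combination overcomes the difference between patients, early-arm entrants are unselected (mean 1) and the ratio becomes 1 / 1.184 = 0.84, in favour of early rituximab.

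**4. How often it would mislead.** Simulation, 4,000 trials per cell, log-rank beyond 1.96, for variance 0.25 / 0.5 / 1:

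| Case | Result |
|---|---|
| Shared frailty, 4×, 65 per arm, second limb alone | early shorter in 5.2 / 8.6 / 11.8% |
| Same, both limbs together | 5.6 / 8.2 / 12.0% |
| Shared, 2×, 65 per arm, both limbs | 3.5 / 3.3 / 3.2% |
| Shared, 2×, 34 per arm, both limbs | 2.1 / 2.2 / 1.7% |
| Patients differ only in rituximab sensitivity, 4×, 65 per arm, second limb | early shorter in 6.3 / 14.1 / 29.5% |
| Patients differ only in the first period, 4×, 65 per arm, second limb | early shorter in 2.6 / 2.8 / 2.8% (no bias) |
| Combination overcomes the difference, 4×, 65 per arm, second limb | early shorter in 2.2 / 1.4 / 0.6%; early longer in 2.8 / 5.1 / 8.9% |

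The first and second rows are separate runs and agree within simulation error. The nominal rate for the second limb is 2.5%. For both limbs together, 2.5% is a ceiling when there is no selection.

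**5. A second, different model.** Assume a normal latent risk that drives residual MRD at 6 months (logistic slope 1.5), a baseline second MRD-free median of 36 months, log-hazard 0.5 per SD, and again no harm. In the 5% v 25% stratum the second-period medians are 18.9 (early) v 23.2 months if the risk acts alike in both arms. They are 34.7 v 23.3 months if residual MRD in the early arm is unrelated to it. The sign again depends on an unknown.

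**The case against.** The strongest reply is that the plan already has the right comparison. The whole-sequence measure appears in 1.1.2 and 6.2, and 1.3.2 calls it the major secondary endpoint. The disputed sentence is rationale, not a test, and secondary analyses are exploratory. This stands as a limit on importance. It does not remove the problem: the exploratory label concerns testing and adjustment, and neither it nor the curves from randomisation withdraws the stated reading or the causal wording in 1.1.2.

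Second, 1.3.2 needs both limbs, and at a twofold rate with shared frailty the full pattern is hardly more frequent than nominal. That also stands; the size depends wholly on assumptions.

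Third, the whole-sequence measure is not neutral about carry-over. Under 6.1 only the cladribine-alone arm may have a second delayed course, so that arm can accrue three periods against two. With no harm, shared frailty, 65 per arm and an assumed 156 months of follow-up, the early arm is significantly shorter on it in roughly 9–17% of trials at fourfold and 20–40% at twofold. This is a genuine difference between strategies rather than selection bias, but it must be disclosed.

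Three stronger readings are tempting and not supported. A reader might infer that the bias must count against early rituximab; nothing in the documents fixes its direction. A reader might infer that the plan treats absence of shortening as reassurance; 1.3.2 states no such converse. A reader might infer that 6.2 and Appendix B flatly contradict each other, because 6.2 counts developing MRD as an event while examples B, E and F run past recurrences. But 6.2 names two endpoints: its event fits time to first MRD, and Appendix B illustrates the sequence. What is missing is a statement of which definition belongs to which.

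**Conclusion.** The point holds as one of interpretation. On its natural reading, the second limb in 1.3.2 compares groups formed after randomisation by an outcome under the influence of treatment. It cannot by itself show whether early rituximab compromises later response. In no-harm simulations with shared frailty and 65 per arm, the misleading two-part pattern occurs in about 5–12% of trials at a fourfold rate and about 3–4% at twofold. With 34 per arm at twofold it is about 2%. Under another plausible assumption the bias runs the other way. These figures rest on assumed medians, rate ratios, frailty and follow-up.

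Whether the word significantly covers both limbs is unclear. If shorter is judged by direction alone, it occurs in about half of trials by chance; that is ordinary null behaviour, not selection. A reader might go further and infer that the trial's efficacy conclusion is compromised. It is not: the 6-month comparison uses all patients as randomised. The point merits a wording change, with medium confidence in its practical weight.

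**What to change.** - **1.3.2:** rest the argument for or against a new standard on the whole-sequence comparison already listed: blood MRD-free survival from randomisation, in all randomised patients as randomised, by stratum.
- **6.2:** give that endpoint one time origin and one event, separate from time to first MRD, and reconcile the Appendix B examples with it. Example A scores >23 months at 24 months, apparently leaving out the time before MRD cleared (24 − 1 = 23). Example D scores >24 months although MRD was positive through month 6.
- **1.1.2 and 1.3.2:** label the delayed-rituximab contrast descriptive and non-randomised, and say that a difference in either direction cannot by itself show whether early rituximab compromises later response.
- **Reporting:** because the arms may differ in the number of delayed courses, give the number of courses per arm, and show the result up to the end of the period after the first delayed course beside the full sequence. That truncated result compares two rituximab courses with one, so neither version should stand alone.

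The cost is a few sentences, with no new data and no change to the primary analysis. The real loss is the causal reading of the relapsed-only contrast. The whole-sequence measure compares strategies and does not test induced resistance.

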
1.3.3 Inability to assume that rituximab should be used with cladribine

Before a trial begins it is optimal for neither arm of a randomized trial to be obviously more advantageous than the other. There are potential advantages and disadvantages of simultaneous vs. delayed rituximab. It is possible, for example, that rituximab could have been more effective when begun at least 6 months after cladribine than concurrently, because by that time masses of tumor cells in the marrow, spleen and lymph nodes, which would present a tumor penetration problem for the rituximab Mab, might be at their minimum size. Secondly, if simultaneous rituximab were to fail to eliminate MRD, it could select for cells deficient in apoptosis and render patients unresponsive to rituximab and other agents when relapse occurs later in the disease course. Moreover, it is possible that the risk of infection could increase with combined use of rituximab and cladribine, since rituximab is known to cause rapid and prolonged (3-6 month) depletion of normal B-cells [57]. While this may not be a significant problem after single-agent short-course rituximab, it may be more problematic with the longer 8-cycle course, particularly after cladribine. Thus, a randomized trial was needed to determine if rituximab should be used with cladribine or delayed until after MRD appears. At this time, it is not considered standard to combine rituximab with cladribine for first-line or second-line treatment of HCL.

